Method 2: The participants will return to the study site and the test product will be applied with the applicator (see application mode). 5 minutes after application, participants will wash the test area according to the washing procedure. This will be repeated after 5 minutes. The water of each washing step (1st and 2nd washing of test area) will be caught separately in a jar and handled as described below (see investigational methods). The test product will be weighed before and after application.

Any remaining test product on the elbow and the hands will be removed using alcohol on a paper towel by the participants themselves.

Method 2

Method 3: The participants will return to the study site and the test product will be applied with the applicator (see application mode). 5 minutes after application, participants will wipe the test area with a paper towel. Afterwards, the test area and hands will be washed according to the washing procedure. The water of the washing step will be caught in a jar and handled as described below (see investigational methods).

The paper towels and test product will be weighed before and after application. Any remaining test product on the elbow and the hands will be removed using alcohol on a paper towel by the participants themselves.

Method 3

As a wash out period, a time frame of at least 2 days will be kept in between each method per participant. No carry over effect of the test product is to be expected due to this washout periods.

CLIMATIC CONDITIONS

During the investigation(s) room temperatures without additional air conditioning will be used.

TEST SCHEDULE

A scheme of the test procedure is given as appendix 1 to protocol.

INVESTIGATIONAL METHOD(S)

The following investigational method(s) will be performed:

TAKING OF WATER SAMPLES for lab analysis

- The water used for the washing sequence will be caught in a jar and will be stirred for 1 minute. Afterwards 3 water samples (approx. 100 ml) will be taken from different locations in the jar (top, bottom and in the middle) with tubes provided by the laboratory.
- A control sample of tap water only, collected prior to the product application, will also be analysed to prove the absence of diclofenac in the tap water used for washing.
- To minimize sample cross-contamination, a fresh pair of gloves will be worn by the technician for each participant.
- Water samples will be stored at room temperature until shipment.

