- The samples will be shipped after the end of each study day to the following address:

- The labeling of the tubes will be as following:

Study Number: CCI

SXXW0X

- Participant No.: XX = 01-33
- Water Sample: W01= Method 1- Hands, W02= Method 1 - Test area,
W03= Method 2 - 1st washing, W04= Method 2 – 2nd washing,
W05= Method 3

Water sample analysis regarding the amount of diclofenac with HPLC will be performed by an external partner laboratory:

The analysis will be performed according to the following steps:

Determination of Diclofenac amount by direct injection:

- If necessary: filtration of the samples through 0.45 µm PTFE (Polytetrafluorethylene) filter.
- Addition of an isotope-labelled standard
- Direct injection and measurement by RP-LC-MS/MS (reverse phase-liquid chromatography–mass spectrometry) in positive ionization mode.

The laboratory will destroy the samples and/or remaining material and document the destruction. The laboratory will provide the study site with a document to confirm the destruction. The destruction will take place 6 weeks after sending the results at the very latest.

ADVERSE EVENT

The investigator and any qualified designees are responsible for detecting, documenting, and reporting events that meet the definition of an adverse event (AE) or serious adverse event (SAE).

Definitions

Adverse Event (AE): An AE is any untoward medical occurrence in a clinical study subject, temporally associated with the use of a study product, including any washout or lead-in product (or medical device), whether or not considered related to the study product.

Serious Adverse Event (SAE): An SAE is any untoward medical occurrence at any dose that results in death, is life-threatening, requires inpatient hospitalization or prolongation of existing hospitalization, results in persistent or significant disability/incapacity, results in congenital anomaly/birth defect, or is otherwise considered an important medical event.

Time Period for Collecting Adverse Event Information

All AEs and SAEs will be collected immediately after a subject provides consent to participate in the study (i.e., by the completion of the ICF) and up until 5 days following last administration of test product (if reported by the subjects).

Recording Adverse Event Information

All AEs and SAEs will be recorded on the AE page of the CRF by the investigator or site staff. AEs should be reported using concise medical terminology.

Reporting of Serious Adverse Events

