The investigator will decide which protocol deviations occurring in the study are assumed to be minor and major before data is analyzed. Valid participants will be defined as enrolled participants who will have finished the study without major deviations from the protocol and who will not have withdrawn their consent. As this is an exploratory study no sample size calculation was performed. The sample size was chosen based on the experience of the study site with this type of study CCI

CCI

Missing data

No replacement of missing data will be performed and the affected assessments will be regarded as lost for analysis.

Demographic data

Demographic variables (age, gender) will be given for the analysis population. Data will be summarized using frequency distributions (number and percentage) for categorical/ordinal variables and mean, standard deviation and range for continuous variables.

Unblinding and derandomization

Not applicable.

Data cleaning

Data cleaning and documentation will be performed according to study sites SOP, performing back-end checks and manual inspections, making self-evident corrections, querying potential data issues, executing necessary data corrections or deletions, tracking queries until resolved, and reviewing corrected data.

Data listing

Raw data

Diclofenac concentration: The mean of all three repeated measurements by participant and water sample (W0X) will be calculated and used as raw data further analysis.

All raw data will be listed by parameter and water sample for valid participants only.

Descriptive data analysis

Summary tables

Descriptive statistics (n, mean, standard deviation, median, minimum, maximum, and 95 % confidence limits) will be given for raw data by parameter and water sample.

Figures

The mean values of raw data will be presented in bar charts with 95 % confidence limits by parameter and water sample.

Statistical data analysis

A significance level of 0.05 (alpha) will be chosen for statistical analysis. Due to the explorative character of this study, no adjustments for multiplicity will be performed.

Pairwise comparison of all water samples will be done by paired t-test on raw data for diclofenac concentration.

The computation of the statistical data will be carried out with a commercially available statistics software (SAS for Windows).

FINAL REPORT

The report will include the following:

PDF report:

Identification of study personnel

Any protocol deviations and/or additional remarks

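### Filtration is optional and the isotope-labelled standard is listed after it, so diclofenac lost on the filter would go uncorrected and, if handling differs between samples, could bias the paired comparisons

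*Combined protocol and SAP*

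**What the plan says.** Under INVESTIGATIONAL METHOD(S), the determination of diclofenac is introduced with "The analysis will be performed according to the following steps". Three steps follow in this order:

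1. "If necessary: filtration of the samples through" a 0.45 µm PTFE filter
2. "Addition of an isotope-labelled standard"
3. "Direct injection and measurement by RP-LC-MS/MS"

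The text does not say when filtration is necessary or who decides. It does not require all wash samples, or all tubes from one jar, to be treated alike.

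On sampling, the same section states: "Afterwards 3 water samples (approx. 100 ml) will be taken from different locations in the jar". The only control it describes is a blank: "A control sample of tap water only, collected prior to the product application, will also be analysed to prove the absence of diclofenac".

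In ANALYSIS OF DATA, under Raw data: "The mean of all three repeated measurements by participant and water sample (W0X) will be calculated". These means then enter paired t-tests between all water samples at alpha 0.05, without multiplicity adjustment. The contents listed under FINAL REPORT do not include which samples were filtered.

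**The concern.** The study exists to quantify diclofenac in rinse water, so analytical recovery acts directly on its main result. An isotope-labelled standard corrects for losses and signal changes that it shares with the analyte. If it is added after the filter, it never passes through the filter and cannot share that loss.

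Two things are at stake. First, the absolute concentration in any filtered sample would read low by the fraction lost. Second, if the share of filtered samples differs between two wash types, part of the difference between them would come from laboratory handling. Mixed handling within a jar would enter the three-tube mean unseen.

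Nothing in the plan would show either effect. A tap-water blank contains no diclofenac to lose, and no spiked recovery sample is described.

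**Working it through.** The documents give no figure for filter loss or recovery, so there is nothing to reproduce. What follows is a sensitivity check.

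**Inputs from the protocol.** Five water samples (W01 to W05), three tubes per jar, 33 participants recruited and about 30 expected to finish, paired t-tests at alpha 0.05. The protocol does not state sidedness; two-sided is assumed.

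**Assumed inputs.** Fractional filter loss L of 2% to 20%; share f of a wash type's samples that is filtered, 0% to 100%; standard deviation (SD) of the paired difference at 20%, 40% or 60% of the mean; equal true means. The SD is held fixed whatever the filtering pattern, which is a simplification.

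**Mean.** With the standard added after the filter, measured mean = true mean × (1 − fL). For two wash types with equal true means:

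measured ratio = (1 − f₂L) / (1 − f₁L)

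**False-positive rate.** The noncentrality parameter of the paired t-test is |f₂ − f₁| × L ÷ (SD as a fraction of the mean) × √30, with 29 degrees of freedom. Example: L = 10%, 0% versus 50% filtered, SD 20%. The shift is 0.5 × 0.10 = 0.05, the noncentrality is 0.05 / 0.20 × √30 = 1.37, and the rejection rate is 0.263.

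| Loss L | Filtered, f₁ vs f₂ | Measured ratio | False-positive rate at SD 20% / 40% / 60% |
|---|---|---|---|
| any | equal shares | 1.000 | 0.05 / 0.05 / 0.05 |
| 2% | 0% vs 100% | 0.980 | 0.083 / 0.058 / 0.054 |
| 10% | 10% vs 30% | 0.980 | 0.083 / 0.058 / 0.054 |
| 5% | 0% vs 50% | 0.975 | 0.102 / 0.063 / 0.056 |
| 10% | 0% vs 50% | 0.950 | 0.263 / 0.102 / 0.073 |
| 20% | 0% vs 50% | 0.900 | 0.754 / 0.263 / 0.143 |

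**Absolute amount.** Equal shares protect the ratio but not the level. If every sample is filtered with 10% loss, every mean reads 1 × 0.10 = 10% low.

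**Tubes within a jar.** If k of the three tubes are filtered, the jar mean is the true value × (1 − kL/3). At L = 10%, one filtered tube gives 1 − 0.10/3 = 0.967 and three give 0.900.

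**Standard added first.** If the standard passes through the filter and is retained in the same proportion as the drug, the factor (1 − L) applies to both and cancels, in the absolute amount and in the comparison.

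**The case against.** The best case against the point is that much of what makes it alarming is inference. A reader might infer that filtration is triggered by visible cloudiness and so falls mainly on the jars with most gel (W01, W02, W03), pulling high values down relative to low ones. The documents do not support this. They mention no visual trigger and do not describe any sample as more turbid. The same washing procedure, with about 1 mL of soap and 2 litres of rinse water, applies to every wash. W05 follows wiping with a paper towel and covers both hands and elbow, so it could as easily be the cloudier sample. No direction can be claimed.

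A reader might also take a loss of 5% to 30% and conclude that a true 2.0-fold contrast would be reported as 1.9-fold (2.0 × 0.95) to 1.4-fold (2.0 × 0.70). The arithmetic is right, but it needs one wash type wholly filtered and the other not at all, and a loss that no document gives.

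The protocol text is also a short summary of an external laboratory's method. That laboratory may hold a validation or procedure covering filter recovery, calibrator treatment and the criterion for filtering. It may filter everything or nothing. And the study is exploratory.

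All of this stands as a limit on size and direction. It does not remove the gap. The listed order leaves filter loss uncorrected, the protocol cites no recovery evidence, and uniform handling is not required.

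**Conclusion.** The point holds in conditional form. As listed, the isotope-labelled standard cannot correct for diclofenac retained on the filter, and the tap-water control would not reveal such a loss. Any loss would lower the absolute amounts in filtered samples. It would bias the paired comparisons only if filtration differs between wash types or between tubes.

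Under the assumptions above, the effect runs from none (uniform handling, as far as contrasts are concerned) through negligible (ratio 0.980 at 2% loss, even with 0% versus 100% filtered) to material (ratio 0.950 at 10% loss with 0% versus 50% filtered). In that last case the false-positive rate is between 0.073 and 0.263, depending on the SD. The direction across wash types is unknown. That filtration will be unequal, or that the filter retains diclofenac at all, is a possibility the plan leaves open and not something it states. The change is worth making because the gap touches the main measurement and is cheap to close.

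**What to change.** - Add the isotope-labelled standard to a measured aliquot before any filtration.
- State one filtration rule and apply it to every W01 to W05 tube and to the control: all filtered or none.
- Flag in the data listing any sample handled differently.
- Check filter recovery in a few soapy rinse-water samples spiked with the product. Moving the standard forward corrects adsorption of dissolved drug. It does not correct drug held in undispersed gel or debris, because a free standard need not be retained with it. Filtering everything makes the comparison fair but, without a recovery check, leaves the absolute amount low by the loss.

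If the analyses have already been run, ask the laboratory for its record of which samples were filtered and for any validation of filter recovery. The protocol has study samples destroyed no later than 6 weeks after results are sent, but recovery can still be tested in freshly spiked rinse water.

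Cost: a change in the order of two steps, up to 33 × 5 × 3 = 495 filters plus the control if all tubes are filtered, and a small recovery experiment. Nothing changes for participants.

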collected.

STUDY POPULATION

A minimum of 33 participants will be recruited for this test from the general population and neighbouring communities of the study site's location so that about 30 participants are expected to finish in the study. Participants who drop-out after randomization into the study will not be replaced. All participants will have a complete understanding of the test procedure.

All below mentioned inclusion, exclusion criteria and instructions for the participants will be checked by a questionnaire before the start of the study and during the study. Conditions developing during the study listed in the exclusion criteria and instructions as well as protocol deviations do not necessarily lead to the participant's exclusion. The investigator decides whether the participant is still eligible.

INCLUSION CRITERIA

- Written informed consent to participate in the study
- Willingness to actively participate in the study and to come to the scheduled visits
- Female and/or male
- From 18 to 70 years of age

EXCLUSION CRITERIA

- Female participants: Pregnancy or lactation
- Drug addicts, alcoholics
- AIDS, HIV-positive or infectious hepatitis
- Conditions which exclude a participation or might influence the test reaction/evaluation
- Participation or being in the waiting period after participation in cosmetic and/or pharmaceutical studies pertaining to the test area
- Cancer not being diagnosed as cured and requiring chemotherapy, irradiation and/or hormonal treatment within the last 2 years
- A previous allergic reaction, sensitivity or intolerance to diclofenac or any of the other ingredients in Voltaren® Schmerzgel forte
- Patients in whom asthma, angioedema, urticaria or acute rhinitis are precipitated by acetyl salicylic acid or other non-steroidal anti-inflammatory drugs (e.g., ibuprofen, naproxen etc.)
- Documented allergies to cosmetic products
- Active skin disease at the test area
- Wounds, moles, tattoos, scars, irritated skin, excessive hair growth, etc. at the test area that could influence the investigation
- Any topical medication at the test area within the last 3 days prior to the start of the study

INSTRUCTIONS FOR PARTICIPANTS

Instructions prior to the start of the study:

The participants will be instructed not to...

- Not applicable

The participants will be instructed to...

- Not applicable

Instructions throughout the course of the study:

The participants will be instructed not to...

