Adverse reactions (if any) that cannot be described by employed scoring scales

Interpretation of data

Figures illustrating the main results

Tables with main results

Tables with descriptive statistics

QA statement

PDF appendices:

List of participants enrolled and completing the study, and participants not analyzed, if any, with reasons

Listing of raw data for all valid participants

Listing of calculated values

Statistical analysis

Amount of test product used

Other electronic files:

Listing of raw data for all valid participants (excel file)

Listing of calculated values (excel file)

SAS files

CORRECTIONS OR ADDITIONS TO THE FINAL REPORT

Corrections or additions to the approved (i.e. signed) version of the final report will be in the form of a discernible second version of the final report or by an amendment. This amendment will clearly identify

the part of the final report that is being added to or corrected, and will be signed and dated by the person responsible.

STORAGE OF DATA

All raw data pertaining to the study will be available for inspection by the sponsor for compliance monitoring. In addition, specified scientists designated by the sponsor may, upon appointment, examine any set of data.

At the study site, all documents related to the study will be stored for at least 10 years and will be either destroyed or returned to the sponsor afterwards, upon consultation with the sponsor. The sponsor will store all documents related to the study for at least 30 years.

QUALITY ASSURANCE

For studies with participants: The study will be conducted, the analysis performed and the report prepared approximating the main principles of Good Clinical Practice (GCP) and in accordance with relevant national regulations and approved protocol(s). The principle requirements of the Declaration of Helsinki will be taken into account to protect the rights, safety and well-being of participants participating in the study.

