If, after a study is underway, it becomes necessary to make changes to the approved protocol(s), the revisions and reasons for changes will be documented. Appropriate corrections, additions, or deletions that are made to the study documentation will be dated, explained (if necessary), and initialed by responsible personnel. Processing of clinical research data and data analysis will involve verification of data integrity and statistical procedures. The final analysis will be done on the basis of the complete data of valid cases, reasons for data exclusion will be given. The final analysis will serve as a basis for the study report.

An independent quality assurance unit will be engaged to audit clinical research studies to identify, evaluate and communicate the state of compliance with applicable protocol(s), and the quality system of the study site. The audit program approved by management will ensure that audits will be performed at regular intervals. Objective evidence pertaining to the correct conduct of studies, the performance of quality control measures for completeness and accuracy of research data, data analysis, and reporting of results will be given and reported to management and to the investigator, as appropriate.

ETHICAL CONSIDERATIONS

For studies with participants, the following ethical consideration will be effective: Authorized medicinal products when used for the approved indication have to be safe products. In this study, no efficacy assessments regarding the effect of the applied medicinal product will be conducted. According to Landesamt für soziale Dienste Schleswig-Holstein Abt. Gesundheits- und Verbraucherschutz, Arzneimittelüberwachung for the assessments of this study no clinical trial according to the German pharmaceutical law is deemed to be necessary.

It is not expected that contact allergy is induced in any participant in this study. However, a sensitization can never be excluded with certainty. Nevertheless the study will be reviewed by an independent institutional review board (IRB) for ethical approval on sponsor's request.

SPONSOR INSPECTIONS/ AUDITS

The sponsor may, upon appointment, visit the study center at any time during and after the study.

DEVIATIONS/ PROTOCOL MODIFICATIONS

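### The only analysis set is completers without a major deviation, so usable sample pairs are discarded, and the deviation classification is not locked before laboratory results are released

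*Combined protocol and SAP*

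**What the plan says.** All references are to the combined protocol and SAP.

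- **ANALYSIS OF DATA, Analysis population.** "Valid participants will be defined as enrolled participants who will have finished the study without major deviations from the protocol". The same sentence adds that consent must not have been withdrawn. No other population is defined in the visible text.
- **QUALITY ASSURANCE** repeats the choice: "The final analysis will be done on the basis of the complete data of valid cases, reasons for data exclusion will be given".
- **ANALYSIS OF DATA, Missing data** works at a finer level: "No replacement of missing data will be performed and the affected assessments will be regarded as lost for analysis".
- **Who classifies deviations, and when.** "The investigator will decide which protocol deviations occurring in the study are assumed to be minor and major before data is analyzed". STUDY POPULATION gives a related discretion over conditions and deviations that arise during the study: "The investigator decides whether the participant is still eligible".
- **ANALYSIS OF DATA, Data listing.** "All raw data will be listed by parameter and water sample for valid participants only".
- **FINAL REPORT** calls for any protocol deviations to be reported, and for this appendix: "List of participants enrolled and completing the study, and participants not analyzed, if any, with reasons".

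Four further facts bear on the point. The study is open label (STUDY DESIGN). Every participant follows the same order, Method 1, then 2, then 3 (TEST PROCEDURE). Samples leave for the external laboratory at the end of each study day (INVESTIGATIONAL METHOD(S)). Dropouts are not replaced (STUDY POPULATION).

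**The concern.** The tests are paired t-tests between water samples, so the natural unit of loss is the pair. The plan instead removes the participant. The assessment-level missing-data rule can never help a non-finisher, because that person is already outside the analysis set. Because the order is fixed, non-finishers always lose the later methods and keep the earlier ones. Someone who stops after Method 2 has complete data for hand against applicator application between Methods 1 and 2, and those data are not used. A deviation at one visit, if called major, likewise discards the unaffected visits.

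The second strand is how exclusions are decided. The person who classifies deviations knows the method used, has no stated criteria, and is bound only to act before analysis. That is looser than acting before results are available. Since the excluded participants' values are not listed, a reader of the report could not re-run a comparison with them included.

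**Working it through.** **Inputs.** At least 33 recruited and about 30 expected to finish (STUDY POPULATION). Five water samples, W01 and W02 from Method 1, W03 and W04 from Method 2, W05 from Method 3 (ASSESSMENT TIMES). Pairwise paired t-tests of all samples at alpha 0.05 (Statistical data analysis); sidedness is not stated, so two-sided is assumed. The plan has no power-based sample size to reproduce. Its recruitment figures imply a loss of 33 − 30 = 3, and 3/33 = 9.1%.

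**Pairs held and used.** Five samples give C(5,2) = 10 comparisons.

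| Last method completed | Samples held | Complete pairs | Pairs used under the plan |
|---|---|---|---|
| Method 1 | W01, W02 | C(2,2) = 1 | 0 |
| Method 2 | W01 to W04 | C(4,2) = 6 | 0 |
| Method 3 | W01 to W05 | 10 | 10 if no major deviation, otherwise 0 |

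With three non-finishers, the discarded participant-pairs number 3 × 1 = 3 if all leave after Method 1, and 3 × 6 = 18 if all leave after Method 2.

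**Completers with a major deviation at one visit.** If it spoils Method 1 or Method 2, three samples remain, giving C(3,2) = 3 usable pairs, two of which involve W05. If it spoils Method 3, four samples remain, giving 6 pairs, none with W05. The plan uses none of these.

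**Precision.** The 95% CI half-width, in units of the SD of the paired difference, is t(0.975, n − 1)/√n.

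- n = 30: 2.045/5.477 = 0.373
- n = 33: 2.037/5.745 = 0.355
- Ratio: 0.373/0.355 = 1.05, in line with √(33/30) = 1.049

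The standardised difference detectable with 80% power moves from 0.503 at n = 33 to 0.529 at n = 30.

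This is a ceiling. It is reached for all six pairs among W01 to W04 only if all three non-finishers complete Method 2. If all three leave after Method 1, only W01 against W02 gains. The four comparisons with W05 gain nothing from dropouts, only from completers who were excluded for a deviation.

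**What the timing safeguard is worth.** As a hypothetical extreme, 200,000 samples of 33 normal differences with true mean zero were simulated, and the 1, 2 or 3 most extreme values on one side were dropped before testing. The two-sided type I error became 7.9%, 13.3% or 21.0% instead of 5%, and the mean shifted by 0.07, 0.12 or 0.17 SD. This shows the sensitivity of the test to deliberate selection. It is not an estimate of what would happen here.

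**The case against.** The case for the plan is respectable. The study is exploratory, the outcome is an external mass-spectrometry assay, and the question is what washes off when each method is carried out as described. A per-protocol set suits that question, and it keeps largely the same people behind every mean in the summary tables and bar charts. Available-pair analysis gives different contrasts slightly different participants. This stands as a reason to keep the completer set, but as a supporting analysis; it does not justify discarding pairs already collected.

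Three stronger readings are tempting, and the documents do not support them.

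- A reader might infer that the population rule and the missing-data rule contradict each other. They do not. They apply in sequence, and the second still operates within the valid set, for instance on a lost tube from a completer.
- A reader might infer that exclusions will depend on known results. The plan gives daily shipment of samples. It does not say when results return or who sees them, and it does require classification before analysis. Early sight is not ruled out, but nothing shows it. Dropout and withdrawal of consent are not the investigator's classification decisions in any case.
- A reader might infer that exclusions are hidden. Deviations are reported, participants not analysed are listed with reasons, and the sponsor may inspect all raw data. STUDY POPULATION also says that deviations need not lead to exclusion. Only the excluded values are missing from the listings.

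Redacted text follows the sample-size sentence in the Analysis population section, so statements about what is absent apply to the visible text only.

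**Conclusion.** The point holds as a modest, worthwhile correction. The stated analysis set discards valid within-participant pairs: up to 6 of 10 for a participant who leaves after Method 2, and all of them for a completer with a single-visit major deviation. It also leaves an open-label classification without criteria or a lock before results.

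The cost in precision is at most about 5% in half-width on the pairs among W01 to W04. That rests on the plan's implied three non-finishers, on all three completing Method 2, and on two-sided 95% intervals. The plan gives no deviation rate, so the further loss from excluded completers cannot be sized. No bias is demonstrated. The weakness is that the written procedure does not exclude it and the planned listings would not let a reader test for it.

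**What to change.** 1. Run each paired comparison on all participants who have both samples, subject to consent, and report n for each contrast.
2. Exclude only the sample or visit that a deviation spoiled, and state in advance what makes a deviation major at that level.
3. Sign and date the deviation classification before laboratory results are released to the investigator.
4. List values for every participant with samples whose consent allows it, flagging those outside the valid set.
5. Keep the valid-completer set as a sensitivity analysis.

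The cost is revised wording, one extra analysis and one sign-off. No new participants, visits or assays are needed. The downside is that the number of participants will differ slightly between contrasts.
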